## 4.2. Interim Analysis and Data Monitoring

An independent iDMC has monitored patient safety during the NI-0501-06 study. The iDMC is composed of relevant experts: pediatric rheumatologist, pediatric oncohematologists, pediatric immune deficiency/infectious disease specialists, a biostatistician, and a specialist in ethics.

The main iDMC responsibility has been to review safety and relevant efficacy data as they were generated, with the objective of determining the benefit/risk profile of emapalumab treatment in the patients enrolled in the study, thus ensuring that no patient was exposed to unnecessary risks.

The iDMC could recommend treatment discontinuation for individual patients as well as temporary study suspension or study termination.

A PK analysis has been conducted when a total of 5 patients were recruited to assess the appropriateness of the proposed dose regimen.

AD-ST-33.04 Effective date: 30-Jun-2017

Version 2.0 | Date 29-Oct-2020 | AD-PR-109.01 Effective date: 26-Jun-2017 Page 18 of 51

No formal interim analyses were planned. However, a descriptive summary of the efficacy and safety results from this open label study has been prepared for presentation at health authority meetings (FDA). Some of these preliminary results have been presented at congresses.

#### 5. Analysis Populations

The following analysis populations are planned for this study:

- All Treated Population (All Treated): The All Treated Population includes all patients who receive any part of an infusion of study drug. In this study, this population corresponds to the Safety population.
- Evaluable Population (EVAL): The EVAL Population includes all patients in All Treated Population who have received a minimum of 3 consecutive infusions of emapalumab, and for whom the diagnosis of background disease sJIA is confirmed (e.g., no evidence for malignancy-related HLH or primary HLH has emerged after enrollment). Should any deviations be considered to significantly impact on efficacy, the impacted patient(s) should be excluded from the EVAL Population.

Inclusion in the EVAL analysis populations will be determined at a data review meeting before database lock. Sobi will review patient level data and a list of subjects for whom the diagnosis of background disease sJIA is confirmed will be provided to the statistician.

The All Treated Population will be the primary population for safety and efficacy endpoints. The EVAL Population will be secondary for the efficacy analysis.

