#### 1. Overview

This statistical analysis plan (SAP) describes the planned analysis and reporting for Sobi AG protocol number NI-0501-06 (A pilot, open-label, single arm, multicenter study to evaluate safety, tolerability, pharmacokinetics and efficacy of intravenous administrations of emapalumab, an anti-interferon gamma (anti-IFN $\gamma$ ) monoclonal antibody, in patients with systemic Juvenile Idiopathic Arthritis (sJIA) or Adult-onset Still's Disease (AOSD) developing Macrophage Activation Syndrome/secondary HLH (MAS/sHLH)).

The study was being conducted in North America and Europe according to 2 original twin protocols (Version 1.0 dated 19 Oct 2017 for North America and Version 1.1. dated 7 Apr 2017 for Europe) and country-specific versions (to take into account requirements from the national ethics committees). The versions previously in use have been recently amended, in January 2020, and the study is currently being conducted according to protocol version 2.0 (with country specific requirements for France and Italy as previously).

This SAP describes the planned analysis for the combined data of the twin protocols, and a single clinical study report (CSR) will present the results from the protocols.

The structure and content of this SAP provides sufficient detail to meet the requirements identified by the Food and Drug Administration, European Medicines Agency, and International Conference on Harmonization of Technical Requirements for Registration of Pharmaceuticals for Human Use: Guidance on Statistical Principles in Clinical Trials. All work planned and reported for this SAP will follow internationally accepted guidelines, published by the American Statistical Association and the Royal Statistical Society, for statistical practice.

The planned analyses identified in this SAP will be included in CSRs, and they may be included in regulatory submissions, or future manuscripts. Also, post-hoc exploratory analyses not necessarily identified in this SAP may be performed to further examine study data. Any post-hoc or unplanned, exploratory analysis performed will be clearly identified as such in the final CSR.

[figure not shown]
The statistical plan described hereafter is an *a priori* plan. It will be submitted to file prior to the database lock pertaining to study NI-0501-06.

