## 3.2. Sample Size

The sample size was not formally calculated. The sample size of approximately 12 evaluable patients (a minimum of 10 sJIA patients) is based on pragmatic considerations, and on the experience acquired from patients with primary HLH treated with emapalumab.

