## 3.3. Study Population

The study population comprises patients of both genders, with sJIA or AOSD, presenting with MAS and having shown inadequate response to high dose intravenous glucocorticoid treatment.

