## 4. Statistical Analysis and Reporting

#### 4.1. Introduction

All study variables in this study are considered to be exploratory, and no hierarchy of endpoints has been specified. The analysis focuses on descriptive statistics and confidence intervals (CIs).

Data processing, tabulation of descriptive statistics, calculation of inferential statistics, and graphical representations will be performed primarily using SAS (release 9.4 or higher).

Continuous (quantitative) variable summaries will include the number of patients (n) with non-missing values, mean, standard deviation, median, minimum, and maximum.

Categorical (qualitative) variable summaries will include the frequency and percentage of patients who are in the particular category or each possible value. In general, the denominator for the percentage calculation will be based upon the total number of patients in the study population, unless otherwise specified.

The minimum and maximum will be reported with the same degree of precision (i.e., the same number of decimal places) as the observed data. Measures of location (mean and median) will be reported to 1 degree of precision more than the observed data and measures of spread (standard deviation) will be reported to 2 degrees of precision more than the observed data.

Percentages will be presented to 1 decimal place, unless otherwise specified.

Unless otherwise indicated, all CIs will be calculated at the 95% CI.

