## 8. Efficacy Analysis

## 8.1. Efficacy Analysis

The following binary efficacy endpoints will be described using counts, proportions, and exact Clopper-Person 95% CI:

- Patients achieving MAS remission by Week 8 after initiation of emapalumab treatment
- Patients for whom at any time during the study glucocorticoids can be tapered
- Patients who tapered steroids to ≤1 mg/kg/day of prednisone equivalent dose
- Patients withdrawn from the study due to lack of efficacy

The following time-to-event efficacy endpoints will be analyzed descriptively:

- Time to first MAS remission
- Time to achievement of permanent glucocorticoids tapering
- Survival time

Summaries will include for each observed time, the survival estimate, failure rate, number of events and the number of patients remaining, also called population at risk. The median, lower quartile and upper quartile estimates of time-to-event and their 95% CI will be tabulated in a separate table. A Kaplan–Meier graph will be presented for each time-to-event endpoint.

The efficacy analysis will be based on the All Treated Population. Efficacy analyses will be repeated for the EVAL Population.

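### SAP Section 5 requires confirmed sJIA for the Evaluable population, so read literally it drops correctly diagnosed AOSD patients from the only secondary efficacy set (low impact)

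*SAP*

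**What the plan says.** SAP Section 5 defines two populations. All Treated is primary for safety and efficacy, and EVAL is secondary for efficacy. EVAL requires at least three consecutive infusions and admits only patients "for whom the diagnosis of background disease sJIA is confirmed". The bracketed example for that condition is that "no evidence for malignancy-related HLH or primary HLH has emerged after enrollment". Patients with deviations judged to affect efficacy significantly are also removed. Membership is settled at a data review meeting before database lock, where the sponsor reviews patient-level data and "a list of subjects for whom the diagnosis of background disease sJIA is confirmed will be provided to the statistician".

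Elsewhere the SAP covers both diseases. Section 1 states that "the study is currently being conducted according to protocol version 2.0", and that version admits AOSD under its own diagnostic criteria (Protocol 4.1.1, criterion 2). Section 3.3 reads "The study population comprises patients of both genders, with sJIA or AOSD". Section 3.2 plans about 12 evaluable patients, of whom at least 10 must have sJIA. The glucocorticoid tapering definition in Section 6.1.7 names both diseases.

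On use, Section 8.1 states that "Efficacy analyses will be repeated for the EVAL Population". Section 11 explains that EVAL was added to check the robustness of the efficacy results and that the Per-Protocol set was removed.

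**The concern.** A patient with confirmed AOSD satisfies the protocol but cannot satisfy a condition that names sJIA only. The condition appears both in the definition and in the instruction from which the set is built, so it is not one stray word.

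The clause's own examples, malignancy-related and primary HLH, are patients who turn out not to have the disease under study. An AOSD patient is not in that position. Applied literally, the clause would add disease type to the exclusions EVAL already combines (exposure, misdiagnosis, deviations). A difference between EVAL and All Treated would then partly reflect which disease the patients had, which is not what a robustness check should measure. The efficacy tables in SAP 14.1 are produced on EVAL, and the errata extend the Kaplan-Meier figures to it. If any AOSD patient is enrolled, all of these would be computed on the wrong set.

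**Working it through.** **Figure to reproduce.** None. SAP 3.2 says the sample size was not formally calculated. The check is textual, followed by bounds on the effect.

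**Passages side by side.**

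| Place | Background disease named |
|---|---|
| Protocol 4.1.1, criterion 2 | sJIA; AOSD separately |
| SAP 3.3 | sJIA or AOSD |
| SAP 6.1.7, tapering | sJIA/AOSD |
| SAP 5, EVAL definition | sJIA only |
| SAP 5, list to the statistician | sJIA only |
| SAP errata, version 2.0 | Section 5 not amended |
| Post-hoc analysis plan | Section 5 not amended |

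**Patients at stake.** At the planned mix, 12 − 10 = 2 patients at most, so the affected share is 0 to 2/12 = 16.7%. With 0, 1 or 2 AOSD patients, EVAL can hold at most 12, 11 or 10.

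**Effect on a response proportion.** Assume 12 treated patients who all meet the other EVAL criteria, m of them with AOSD, and x responders of whom k have AOSD. Then

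EVAL − All Treated = (x − k)/(12 − m) − x/12.

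If every AOSD patient responds (k = m), this equals −m(12 − x)/[12(12 − m)], which is lowest at x = m, giving −m/12. If none responds (k = 0), it equals xm/[12(12 − m)], which is highest at x = 12 − m, giving +m/12. The bounds are therefore ±2/12 = ±16.7 points for m = 2 and ±1/12 = ±8.3 points for m = 1.

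The response counts below are assumed. Intervals are exact Clopper-Pearson 95%, the method in SAP 8.1.

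| m | All Treated | k | EVAL, literal | Difference (points) |
|---|---|---|---|---|
| 2 | 9/12 = 75.0% (42.8–94.5) | 2 | 7/10 = 70.0% (34.8–93.3) | −5.0 |
| 2 | 9/12 = 75.0% | 0 | 9/10 = 90.0% (55.5–99.7) | +15.0 |
| 2 | 6/12 = 50.0% (21.1–78.9) | 2 | 4/10 = 40.0% (12.2–73.8) | −10.0 |
| 2 | 6/12 = 50.0% | 0 | 6/10 = 60.0% (26.2–87.8) | +10.0 |
| 2 (bound) | 2/12 = 16.7% (2.1–48.4) | 2 | 0/10 = 0% (0–30.8) | −16.7 |
| 2 (bound) | 10/12 = 83.3% (51.6–97.9) | 0 | 10/10 = 100% (69.2–100) | +16.7 |
| 1 (bound) | 1/12 = 8.3% | 1 | 0/11 = 0% | −8.3 |
| 1 (bound) | 11/12 = 91.7% | 0 | 11/11 = 100% | +8.3 |

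In every two-AOSD row the EVAL interval contains the All Treated estimate.

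**The case against.** The strongest reply is that the harm may never arise. No document gives an AOSD count, and the protocol sets a minimum for sJIA but none for AOSD. The superseded protocol text admitted only sJIA patients under 18, and SAP Section 1 dates the amendment to January 2020. SAP 7.2 still describes a population of children. Having no AOSD patient is plausible. This stands, and the harm is conditional on enrolling one.

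Second, the sJIA-only wording looks like shorthand carried over from that earlier text, and the data review meeting would have to choose to exclude a correctly diagnosed patient. That may be how it works out, but the text instructs the meeting to list confirmed sJIA and gives it no licence to read more broadly. Including AOSD patients would depart from the written rule, in an open-label study where efficacy summaries have already been prepared and some presented (SAP 4.2).

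Third, the word evaluable in SAP 3.2 may be inherited. The superseded protocol used it for sample size and replacement without defining an Evaluable set. This weakens SAP 3.2 as evidence of an internal contradiction. The conflict with Protocol 4.1.1 and SAP 3.3 does not depend on it.

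Fourth, the ±16.7-point bounds need the AOSD patients to be the only responders or the only non-responders, which is unlikely. Listings 16.2.3.1 and 16.2.6.1 would also let a reader trace each excluded patient and outcome. Both points limit the impact but do not make the definition right.

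**Conclusion.** The concern holds. SAP Section 5 is wrong as written, and its impact is low. Read literally, it excludes eligible, correctly diagnosed AOSD patients from the set meant to test robustness. At the planned mix this is 0 to about 2 of approximately 12 patients. With two AOSD patients, the examples at 50% and 75% response move EVAL by −10 to +15 points. These sizes assume 12 treated patients who all meet the other EVAL criteria. Because the planned number is approximate, two is a planning figure and not a hard cap.

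All Treated results are untouched. SAP 4.1 states that "All study variables in this study are considered to be exploratory" and sets no endpoint hierarchy. The point is worth correcting but does not threaten the study's main conclusions.

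**What to change.** Before database lock, amend both sentences of SAP Section 5, for example through the errata, so that the confirmed background disease is sJIA or AOSD. Leave the other EVAL criteria as they are. If an sJIA-only set is intended, state that, give the reason, and label it an sJIA subgroup rather than the robustness set.

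The cost is two added words in each of two sentences, or a short statement that the restriction is intended and why. No new data are needed and All Treated does not change.

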## 6. General Issues for Statistical Analysis

## 6.1. Statistical Definitions and Algorithms

#### 6.1.1. Baseline

The last observation recorded prior to the first dose of emapalumab will be used as the baseline observation for all calculations of change from baseline.

## 6.1.2. Adjustments for Covariates

Not applicable.

## 6.1.3. Multiple Comparisons

Not applicable.

AD-ST-33.04 Effective date: 30-Jun-2017

Version 2.0 | Date 29-Oct-2020 | AD-PR-109.01 Effective date: 26-Jun-2017

### 6.1.4. Handling of Dropouts or Missing Data

An additional patient will be recruited for any patient who withdraws from the study for reasons other than safety or lack of efficacy to ensure a sample size of approximately 12 patients across North America and Europe.

No imputation of missing data will be performed. However, for MAS remission, if one or more laboratory data are unavailable within the visit window, the LOCF approach will be used. Partial date assumptions for the definition of TEAEs are described in Section 6.1.8

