### 12.3.5 Missing Data

No imputations of missing data will be performed. However, the following rules will be applied to ensure that all patients can be included in the final analysis:

- patients who are withdrawn from the study prior to Week 8 because of safety concerns or poor efficacy will be classified as non-responders from the time of their withdrawal in all

analyses of response status, and their data will be censored at time of withdrawal in all time-to-event analyses. For continuous endpoints in such patients, all analyses for time points beyond the point of withdrawal will exclude missing data for these patients.

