## 6.1.5. Analysis Visit Windows

Statistical analyses will be based on scheduled visits as collected in the case report form (CRF) realigned on study days, which are defined based on the date of first emapalumab infusion (SD0) as follows:

Study Day = date of interest - date of first emapalumab infusion.

The following rules will be applied for MAS remission and glucocorticoid tapering.

- For the assessment of MAS remission and glucocorticoid tapering at Week 8, the SD56±5 days analysis period will be considered. Where several such observations occur in this time window, the one closest to SD56 will be selected. If there are 2 such observations that are equidistant from SD56, the observation that is after SD56 will be selected.
- For the assessment of time to MAS remission, see Section 6.1.7.

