• by at least 50% of the equivalent dose of prednisone administered at emapalumab treatment start (in those patients who present with MAS at sJIA/AOSD onset).

The daily equivalent dose of prednisone will be compared with the daily equivalent dose of prednisone at SD0.

AD-ST-33.04 Effective date: 30-Jun-2017

Version 2.0 | Date 29-Oct-2020 | AD-PR-109.01 Effective date: 26-Jun-2017

Page 23 of 51

If it is not possible to establish if a patient has been treated for sJIA/AOSD or not before study start for all patients, or if it is not possible to retrieve glucocorticoids dose administered before the occurrence of MAS for all patients who already are treated for sJIA/AOSD, the glucocorticoids tapering endpoint will be changed. In this case the endpoint will be: "glucocorticoids permanently tapered at any time during the study by at least 50% of the equivalent dose of prednisone administered at emapalumab treatment start (SD0).

If glucocorticoid dosing data are unavailable at a given time point, the assumption that dose has not been further tapered from the previous available observation will be made. Glucocorticoid doses will be calculated as (prednisone-equivalent) mg/kg/day.

- MAS remission = resolution of clinical signs and symptoms according to the Investigator (MAS clinical signs and symptoms score ≤ 1) AND normalization of laboratory parameter relevant to MAS as follows:
  - White blood cell count (WBC) and platelet count above the lower limit of normal (LLN)
  - Lactate dehydrogenase (LDH) below 1.5 upper limit of normal (ULN)
  - Alanine aminotransferase/aspartate aminotransferase (ALT/AST) below 1.5 ULN
  - Fibrogen higher than 100 mg/dL
  - Ferritin level decreased by at least 80% from values at screening or baseline (whichever is higher) or below 2000 ng/mL, whichever is lower

If one or more laboratory data are unavailable within the visit window, the LOCF approach will be used.

- MAS remission by week 8 = patients who meet MAS remission conditions in the period SD56  $\pm$  5 days regardless the time of first MAS remission or its duration.
- Survival:

Time to death = date of death - date of first emapalumab infusion + 1

Patients who survive to the end of the study will be censored at the date of last contact. In case in which a patient withdrew consent the censoring date will be the date of withdrawal of consent.

• Time to MAS remission:

AD-ST-33.04 Effective date: 30-Jun-2017

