		"4) Select the weight in kg from the physical examination visit closest to the glucocorticoids administration date. If there are 2 such observations that are equidistant from the glucocorticoids administration date, the first observation will be selected. Prior to first treatment administration, the weight at screening will be selected."
Section 6.1.7 – Derived variables/ Steps to calculate the prednisone equivalent dose (mg/kg/day) and total daily doses	No specification of time frame for calculation of equivalent prednisone dose or total daily doses of anakinra, canakinumab, ciclosporin, etoposide, methotrexate, and tocilizumab.	To add detail on when equivalent daily dose of prednisone, and daily total doses of anakinra, canakinumab, ciclosporin, etoposide, methotrexate, and tocilizumab will be derived.
of anakinra, canakinumab, ciclosporin, etoposide, methotrexate, and tocilizumab		Specifications added: "Equivalent daily dose of prednisone, and daily total doses of anakinra, canakinumab, ciclosporin, etoposide, methotrexate, and tocilizumab will be derived from study day -180 until the end of the study."

[figure not shown]
 Version 2.0
 Date 22-Jul-2021
 AD-PR-109.02
 Effective date: 17-Aug-2020
 Page 8 of 18

Section 6.1.7 - "where the conversion factor is:  Derived 1 for prednisone	The use of dexamethasone was
variables/ Conversion factor for derivation of equivalent dose of prednisone  1.25 for methylprednisolone 1 for prednisolone"	not considered initially and should be added as administered to some patients.  /  Corrected to "where the conversion factor is:
	1 for prednisone
	1.25 for methylprednisolone
	1 for prednisolone 6 for dexamethasone"
Section 6.1.7 - Derived variables/ MAS remission  "The MAS remission evaluation is based on combination of assessments, including Investigator assessment and laboratory finding The latest date of assessments, within the view window of $\pm$ 3 days around the planned day the visit, will be used for the calculation of time to MAS remission."	To clarify assessment handling for the MAS remission. Currently in the SAP, it specifies "If one or more laboratory data are unavailable within the visit window" but no details on the visit windows.  /  Updated to: "The MAS remission evaluation is based on a combination of assessments, including Investigator assessment and laboratory findings, and will only be calculated if the Investigator assessment has been

[figure not shown]
 Version 2.0
 Date 22-Jul-2021

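### The readable SAP text sets no limit on how old a carried-forward laboratory value may be when it completes a Week 8 MAS remission

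*SAP*

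**What the plan says.** **Remission.** SAP 6.1.7 requires two things together: "resolution of clinical signs and symptoms according to the Investigator (MAS clinical signs and symptoms score ≤ 1) AND normalization of laboratory parameter". The laboratory half covers WBC, platelets, LDH, ALT/AST, fibrinogen and ferritin.

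**Week 8.** SAP 6.1.5 states: "For the assessment of MAS remission and glucocorticoid tapering at Week 8, the SD56±5 days analysis period will be considered". SAP 6.1.7 then defines remission by Week 8 as "patients who meet MAS remission conditions in the period SD56" plus or minus 5 days, that is SD51 to SD61.

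**Missing laboratory values.** SAP 6.1.4 first rules out imputation, then makes an exception for remission: "if one or more laboratory data are unavailable within the visit window, the LOCF approach will be used". SAP 6.1.7 repeats the rule just above the Week 8 definition. The rule works component by component and could cover all of them.

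**Errata v2.0.** The entry for SAP 6.1.7 rewrites assessment handling for MAS remission. It adds that remission "and will only be calculated if the Investigator assessment has been", and in the copy reviewed the sentence stops there. The errata does not list 6.1.4 as amended. Its change history describes this entry as an update of visit-window rules.

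**Protocol 12.3.5.** "No imputations of missing data will be performed". The only special rule there concerns patients withdrawn before Week 8 for safety or poor efficacy, who count as non-responders. SAP Section 11, which lists changes from the planned analysis, does not mention LOCF and says that no further changes are planned.

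**The concern.** Week 8 remission is defined as a state in an 11-day window, and half of that definition is laboratory normalisation. The carry-forward rule lets the laboratory half be met by results from outside the window, with no stated bound on how far outside. A patient who normalised earlier, is scored by the Investigator at Week 8 and has no laboratory result then would count as in remission on old evidence. Whether the laboratory picture held up after the infusions ended is part of what a Week 8 assessment should show.

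Two further points make this worth settling. The departure from the protocol's missing-data rule is not declared where the SAP lists its departures. And a value missing at a single time point is not treated as a protocol deviation (protocol 8.1, SAP 7.2), so the deviation listing would not reveal it.

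**Working it through.** The plan gives no figure to reproduce: SAP 3.2 says that the sample size was not formally calculated. The check has three parts.

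**1. Age of a carried value.** Inputs: Week 8 window SD51–SD61 (SAP 6.1.5); weekly visits at SD35, SD42, SD49 and SD56 (protocol 8.1 and Table 2); laboratory tests at every visit (protocol 8.4); planned last infusion by SD28 (protocol 5.2).

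Age = day of the Week 8 assessment − study day of the source visit.

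| Source visit | At SD51 | At SD56 | At SD61 |
|---|---|---|---|
| SD49 | 2 | 7 | 12 |
| SD42 | 9 | 14 | 19 |
| SD35 | 16 | 21 | 26 |
| SD28 | 23 | 28 | 33 |
| SD15 | 36 | 41 | 46 |

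These are nominal days. The 2-day visit tolerance after SD28 can shift each follow-up source visit by up to 2 days.

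**2. What must be missing.** LOCF takes the most recent earlier value of that analyte.
- SD49 is used if the analyte is missing only in the Week 8 window.
- SD28 is used only if the analyte is missing at SD35, SD42, SD49 and in the Week 8 window: four consecutive scheduled visits.
- If treatment is prolonged, fewer gaps are enough. With a last infusion at SD42, for example, an SD42 value is used after two gaps (SD49 and Week 8).

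**3. Effect on the rate.** SAP 8.1 specifies exact Clopper-Pearson 95% intervals. Take N = 12 as an assumption (the SAP says approximately 12); the counts are illustrations.

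One patient = 1/12 = 8.3 percentage points.

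| Carried remission counted | Not counted |
|---|---|
| 8/12 = 66.7% (34.9–90.1) | 7/12 = 58.3% (27.7–84.8) |
| 10/12 = 83.3% (51.6–97.9) | 9/12 = 75.0% (42.8–94.5) |

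**Direction.** If the last available value was normal, the patient keeps the laboratory half of remission with no new evidence. If it was abnormal and the patient has since normalised, LOCF wrongly denies remission.

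**The case against.** - **The errata may already deal with this.** Its rationale refers to this same LOCF sentence and notes that the visit windows were not detailed. The replacement text is incomplete only in the copy reviewed, and that is not a gap in the plan. This stands: the absence of a limit is established for SAP 2.0 and the readable errata, and no further.
- **A reader might infer that old laboratory values alone can make a Week 8 remission.** They cannot. An Investigator score of 1 or less is also required, and the errata ties the calculation to the Investigator assessment. A missed Week 8 visit with no such assessment should not yield a carried remission.
- **A reader might infer that on-treatment values will commonly count.** On the planned schedule that takes four consecutive gaps in one analyte. The ordinary carry is one week, from off-treatment SD49. Gaps at two consecutive time points also lose their exemption from being protocol deviations.
- **A reader might infer that LOCF hides laboratory relapse in general.** It acts only where a value is missing. If an analyte's latest available follow-up value is abnormal, that value is carried and denies remission. Protocol 5.3 also regards reactivation after remission as very unlikely, although sections 10.3.1 and 11.2.1 provide for it.
- **A reader might take SAP 6.1.9 as predicting missing data.** It lists missing endpoints and visits due to COVID-19 as items to summarise and does not say how many are expected.
- **The SAP may refine the protocol, and every variable is exploratory.** Protocol section 12 leaves full details to the SAP, which states the LOCF rule openly. Counting a patient with missing values as not in remission is also a form of imputation.

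These points make the problem less frequent. None of them supplies a limit, and LOCF is still not declared in SAP Section 11.

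**Conclusion.** The point holds in a limited form. In the readable text, nothing bounds the age or source visit of a carried remission laboratory value. With a qualifying Investigator score at Week 8, results from before SD51–SD61 can complete a Week 8 remission. The likely case is mild (SD49, 2–12 days old). The serious case (SD28 or earlier, at least 23 days old) needs four consecutive gaps on the planned schedule, or fewer with prolonged treatment.

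The size is 8.3 percentage points per affected patient at an assumed N = 12. The documents do not show that any patient is affected, and the net direction over all patients cannot be fixed in advance. The conclusion assumes that the truncated errata entry adds no limit, which the sponsor can confirm directly. The change is a cheap improvement to a stated rule, and the finding does not show that the remission rate will be wrong.

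**What to change.** 1. Confirm the full errata wording for MAS remission. If it already limits carried values, cite that limit in SAP 6.1.4 and 6.1.7.
2. Otherwise, in both sections, allow a missing remission laboratory value to be replaced only from the immediately preceding scheduled visit (SD49 for Week 8). If that value is missing too, count the patient as not in remission at that visit.
3. Apply the same one-visit limit to time to first remission.
4. In Table 14.2.1, add two sensitivity rows: remission with unrestricted LOCF, and remission with every laboratory component observed in the window.
5. In Listing 16.2.6.2, already planned in the post-hoc analysis plan, flag each carried value with its study day.
6. In SAP Section 11, declare LOCF as a change from protocol 12.3.5.

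The cost is a few sentences, one flag and two table rows. The remission rate may be slightly lower, and a patient who is in remission but lacks laboratory values may be counted as not in remission. The sensitivity rows show how much that matters.
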